7 STUDY DESIGN

This study will use both retrospective and prospectively collected data to develop and test an algorithm to identify patients in hospital with acquired bleeding.

The algorithm will be developed using retrospective data from patients admitted to one hospital over a ten year period. The algorithm will be refined using prospective data collected over a three month period and its accuracy tested prospectively in the final 3 months of the study.

In this latter period, we will also assess the feasibility of consenting patients for the sequestering and subsequent analysis of their left-over blood samples, for additional tests of blood clotting.

8 PARTICIPANT IDENTIFICATION

8.1 Study Participants

In both the retrospective and prospective cohorts, we will screen all adult patients admitted to Oxford University Hospitals NHS Foundation Trust for signs of bleeding.

8.1.1 Retrospective cohort

Inclusion Criteria

- Adults aged between 16 and 110
- Admitted to hospital (OUH) or attended the emergency department between 1/3/2011 to 31/8/2022

Exclusion Criteria

- Patients who inform us directly that they do not wish their records used in this research study
- Patients who have completed the NHS Opt-out.

8.1.2 Prospective cohort

Inclusion Criteria

- Adults aged between 16 and 110
- Admitted to hospital (OUHFT) or attended the emergency department between 1/10/2021 to 31/8/2022

Exclusion Criteria

- Patients who inform us directly that they do not wish their records used in this research study
- Patients who have completed the NHS Opt-out.

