3 SYNOPSIS

Study Title	RE-BLEED: A digital platform for identifying bleeding patients: a feasibility study
Internal ref. no. / short title	RE-BLEED
Study registration	The study will be registered on clinicaltrials.gov
Sponsor	University of Oxford
Funder	Oxford BRC
Study Design	Study incorporating database analysis, cohort observation and laboratory study
Study Participants	Patients with actual or suspected acquired bleeding
Sample Size	
Retrospective data Up to 1,750,000 patient admissions (up to 10 years of admissions)
 
Prospective data Up to 87, 500 will be screened by the digital platform to identify those who may have bled during the six-month recruitment period. Research nurses will review

	electronic records of patients with potential bleeding (identified by the digital platform), with the aim of gaining consent from at least 50 in the last three months of the study.		
Planned Study Period	1/10/2021 to 31/8/2023		
Planned Recruitment period	Retrospective data from the period: 1/3/2011 to 31/8/2022 Prospective study: 1/10/2021 to 31/8/2023		
	Objectives	Outcome Measures	Timepoint(s)
Primary	To test whether a digital platform can efficiently identify patients who have suffered a bleeding event and are willing to consent for the routine blood samples to be used in research.	At least 200 patients correctly identified as having suffered bleeding, of which 40 (20%) provide consent	End of study
Secondary	
 1. To conduct a Delphi process with an expert panel to identify criteria that could be applied in the electronic patient record to identify patients with acquired bleeding 2. To use 10 years' of retrospective data to map bleeding criteria to appropriate data fields within the electronic patient record data sources 3. To encode bleeding criteria into a real-time "algorithm" and display results within a digital web-based platform 4. To measure and refine the accuracy of the algorithm, by 	
 1. List of bleeding criteria 2. Bleeding criteria mapped to appropriate data fields on the electronic patient record 3. Digital platform capable of identifying bleeding patients in real-time 4. Algorithm accuracy before/after refinement 5. List of unique challenges faced by the laboratory team during blood sample retention and analysis 6. Numbers of samples retained and additional blood clotting and endothelial factor results captured from the retained samples. 	End of study

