- Research nurses will use the interface to identify (up to 200) patients who are potentially bleeding and review their free-text notes in the electronic patient record, notifying attending clinicians when there is no documentation of bleeding. Using the additional clinical information in patients’ notes, the nurses will record whether they agree with the output of the algorithm. Where the algorithm has incorrectly identified patients as having bled, the nurses will record the reasons for bleeding based on the clinical information in the notes.
- The expert panel will review the results of the notes review and refine the algorithm to increase its specificity.
- The expert panel will not have any access to confidential patient information.

9.2 Consent patients identified by system for use of surplus routine blood samples in research analysis.

In the final three months of the study, we will prospectively test the accuracy of the algorithm and the feasibility of using the real-time platform for consenting patients to use their data and routine blood samples for future research.

When the algorithm identifies that a patient has met the criteria for bleeding, the platform will:

- Allocate the patient a RE-BLEED study ID.

- Electronic Hospital Record (EHR) data for this entire encounter will be retained in the study database and when the encounter ends the record will be pseudo-anonymised.
- A notification will be sent to the main hospital laboratory requesting that their (left-over) blood samples, once all clinical testing has been completed as part of routine clinical care, be retained for use in the study, pending patient consent. Where consent is not given, the samples will be destroyed as per local protocols.

In order to be able to screen all patients in the hospital, the system must collect data for all adult patients from their admission to their discharge. The records of adult patients admitted to the hospital who do not meet the eligibility at any point during their admission will be destroyed at the point they are discharged from hospital.

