9.4.3 Patients with capacity to consent

Formal written consent will be sought from a subset of patients to analyse surplus clinical blood samples. This will be conducted by group of experienced research nurses.

Patients with the physical and mental capacity to give informed consent will be approached in person during the first 28 days following their episode of bleeding and it will be explained to the patient that they have already had blood samples sent for storage. It will be made clear that these samples have not yet been analysed and that these samples will be destroyed if they do not agree to the samples being used.

For any patient where a sample was retained with the intent to be used in the study but the patient did not regain capacity within 28 days, information will be provided to either a personal or a professional consultee for advice about the research use of the sample (see next section).

After this period has past, if consent has not been obtained, all samples will be destroyed.

Patients or their personal or professional consultee will be provided with:

- RE-BLEED patient information leaflet
- RE-BLEED consent form

The RE-BLEED study documentation will detail no less than: the nature of the study; what it will involve for the participant; the implications and constraints of the protocol; the known side effects and any risks involved in taking part. It will be clearly stated that the participant is free to withdraw from the study at any time for any reason without prejudice to future care, without affecting their legal rights, and with no obligation to give the reason for withdrawal.

The participant or consultee will personally sign and date the latest approved version of the Informed Consent form or Consultee Declaration.

The participant, or their consultee, will be allowed a maximum of 28 days to consider the information, and the opportunity to question the Investigator, their GP, or other independent parties to decide whether they will participate in the study.

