9.8 Definition of End of Study

The end of study is the point at which all the study data has been entered and queries resolved.

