11.2.2 Prospective data

Up to 87,500 records will be screened by the digital platform to identify those who may have bled over 2 three-month periods.

In the first three-month period, research nurses will review electronic records of patients with bleeding (identified by the algorithm), we estimate around 250 will experience a bleeding event. Assuming the algorithm has a sensitivity of 80%, we plan to review 200 electronic records.

In the second three-month prospective period, research nurses will approach patients for consent. Based on the assumption that 200 patients will also be identified by the algorithm in this period, we will aim for at least 40 (20%) of patients to consent to their participation.

We will assess the efficacy of the sample retention process being used by the study. This will include the number of samples successfully retained, the number of additional clotting laboratory resulted gained from these samples and any feedback from the laboratory staff regarding challenges they faced.

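### Prospective eligibility closes on 31/8/2022 in section 8.1.2, but the synopsis recruits the same cohort until 31/8/2023

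*Protocol*

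**What the plan says.** Three sets of statements bear on this point.

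- **Eligibility.** Section 8.1.2 includes adults "Admitted to hospital (OUHFT) or attended the emergency department between 1/10/2021 to 31/8/2022".
- **Recruitment and study period.** The planned recruitment row of the synopsis reads "Prospective study: 1/10/2021 to 31/8/2023". The planned study period row carries the same two dates.
- **Timing of the test and consent phase.** The synopsis describes research nurses reviewing records "with the aim of gaining consent from at least 50 in the last three months of the study". Section 7 says the algorithm will have "its accuracy tested prospectively in the final 3 months of the study". Section 9.2 says "In the final three months of the study, we will prospectively test the accuracy of the algorithm" and couples this with the feasibility of consent. Section 11.2.2 says "In the second three-month prospective period, research nurses will approach patients for consent" and sets a target of 40 of 200.

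Two further statements affect how the phase can be placed in time. Section 9.8 says "The end of study is the point at which all the study data has been entered and queries resolved". Section 9.4.3 has patients "approached in person during the first 28 days following their episode of bleeding". No section gives calendar dates for either three-month period.

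(The synopsis figure of 50 consents differs from the 40 used elsewhere. That is a separate matter and plays no part here.)

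**The concern.** The admission date is an operative inclusion criterion. It decides who may be screened, whose record and left-over samples may be kept, and who may count towards the consent part of the primary outcome (section 6: 200 correctly identified, 40 consenting).

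For a patient admitted on or after 1/9/2022 the two passages give opposite instructions. Under section 8.1.2 the patient is ineligible, and section 9.2 has the records of ineligible patients destroyed at discharge. Under the synopsis the patient is within the recruitment period.

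If the final phase runs near the synopsis end date, every newly admitted patient approached for the consent target would fail the written criterion, and each enrolment would be an eligibility deviation. If the phase was meant to run inside the section 8.1.2 window, the synopsis misstates when the study recruits and ends.

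**Working it through.** **Inputs**

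| Item | Value | Source |
|---|---|---|
| Prospective eligibility | 1/10/2021 to 31/8/2022 | 8.1.2 |
| Prospective recruitment | 1/10/2021 to 31/8/2023 | Synopsis |
| Study period | 1/10/2021 to 31/8/2023 | Synopsis |
| Retrospective window | 1/3/2011 to 31/8/2022 | Synopsis and 8.1.1 (agree) |
| Prospective activity | two three-month periods, 87,500 records | 11.2.2 |
| Annual admissions | 175,000 | 11.2.1 |

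**The plan's own figures.** 175,000 × 6/12 = 87,500, so the screening number does correspond to six months of activity. In the same section 250 × 0.80 = 200 and 200 × 0.20 = 40. These figures reproduce. The problem is confined to the dates.

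**Lengths, counting both end days**

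- Eligibility window: 335 days.
- Synopsis recruitment window: 700 days.
- Difference: 700 − 335 = 365 days. So 365/700 = 52% of the synopsis recruitment period lies after eligibility has closed.

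**Reading (a): the final phase is counted back from 31/8/2023.** The phase is 1/6/2023 to 31/8/2023, which is 30 + 31 + 31 = 92 days. It starts 274 days after 31/8/2022, so its overlap with the eligibility window is 0 of 92 days.

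The phase may end before 31/8/2023, because the study ends only once data are entered and queries resolved, and because consent may take up to 28 days. Let L be the number of days from the end of the phase to 31/8/2023. The protocol does not state L, so it is varied here as an assumption. The phase then starts on 1/6/2023 minus L days, and

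overlap = max(0, L − 273), up to a maximum of 92.

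| Assumed L (days) | Phase | Days inside 8.1.2 |
|---|---|---|
| 0 | 1/6/2023 to 31/8/2023 | 0 |
| 28 | 4/5/2023 to 3/8/2023 | 0 |
| 90 | 3/3/2023 to 2/6/2023 | 0 |
| 180 | 3/12/2022 to 4/3/2023 | 0 |
| 274 | 31/8/2022 to 30/11/2022 | 1 |
| 319 | 17/7/2022 to 16/10/2022 | 46 |
| 365 | 1/6/2022 to 31/8/2022 | 92 |

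Close-out would have to take about nine months before a single day of the phase fell inside the window, and a full year before all of it did.

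**Reading (b): the phase lies inside the section 8.1.2 window.** The 335 days can hold both three-month periods, so no recruitment is lost. The phase then ends by 31/8/2022, at least 365 days before the end date in the synopsis. On the synopsis dates it is not in the final three months of the study.

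**Can the gap be admission first and consent later?** A patient who bleeds on 31/8/2022 can be approached until 28/9/2022. That is 365 − 28 = 337 days short of 31/8/2023. A bleed late in a long stay could stretch this for a few patients, but it cannot account for an extra year of recruitment.

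**The case against.** The best defence is that neither date range describes continuous recruitment. The synopsis itself speaks of a six-month recruitment period, and section 11.2.2 of two three-month periods, so both ranges may be outer limits around six months of work. The synopsis range for prospective recruitment is identical to the study period, which suggests a planning envelope. On that view an admission window nested inside a longer envelope is untidy but workable, and the final three months means only the second of the two prospective periods. Section 9.8 helps this view, since patient contact is unlikely to run to the last day of a study that ends when queries are resolved.

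A further argument is that this looks clerical. The latest protocol version is dated 15/08/2022, 16 days before the section 8.1.2 cut-off, and extended the timeframe, so one date may simply not have been carried through.

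Part of this stands. The zero overlap is conditional on how the phase is placed, the values of L are assumptions, and on reading (b) no recruitment is lost. The defence does not remove the contradiction. The synopsis labels its dates as a recruitment period, in a row separate from the study period. The retrospective dates in that same row match section 8.1.1 exactly, so the two places are evidently meant to agree. A likely clerical origin does not tell staff whether the extension covered new admissions or only completion of the study.

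**Conclusion.** The concern holds. Two current passages give prospective end dates 365 days apart, and nothing in the protocol reconciles them. With the accuracy test and consent work placed in the final three months of the study, the two passages cannot both be right as written.

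Counted back from the synopsis end date, 0 of the 92 days of that phase are inside the eligibility window, and this stays so for any close-out lag up to 273 days. If the phase was intended to fall inside the window, the error is in the synopsis and no recruitment is lost. Which of these applies depends on calendar dates the protocol does not give.

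The point needs correcting because the date is an inclusion criterion for the phase that yields the consent part of the primary outcome.

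**What to change.** Reconcile section 8.1.2 and the synopsis to a single prospective end date that covers the final three-month test and consent phase. If the synopsis reflects the intention, section 8.1.2 should read 1/10/2021 to 31/8/2023. If section 8.1.2 reflects the intention, the recruitment and study period rows of the synopsis should be corrected to fit it.

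It would also help to give calendar dates for the two three-month periods of section 11.2.2, or to tie them to a stated milestone if the platform build makes fixed dates impractical. This addition is useful but not essential to removing the contradiction.

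The cost is a wording amendment to the protocol: one end date in section 8.1.2 or the dates in the synopsis. The outcome, sample size and analysis do not change.

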9 PROTOCOL PROCEDURES

9.1 Algorithm development and validation

- Conduct a modified Delphi process using a panel of clinical experts to identify a set of starting criteria (algorithm) e.g. transfusion request or absolute/drop in Hb. In the first instance, we will aim to agree broad criteria that maximise the sensitivity of the algorithm.
- The Clinical Data Warehouse (CDW) is a digital resource within the Oxford University Hospitals NHS Trust (OUH) that will provide up to 10 years of retrospective anonymised patient data to the study. This dataset will comprise demographics and diagnostic/therapeutic codes, hospital locations, admission/discharge timings as well as laboratory results, radiology reports, blood product usage and operative management and outcomes. All data will be time-stamped.
- Using this retrospective patient data, we will develop an algorithm by mapping criteria identified by the Delphi process to routinely-collected data sources. We will combine these mapped criteria into a single algorithm to identify bleeding patients. We will assess its sensitivity to identify patients who have received treatments/investigations for bleeding (e.g. urgent endoscopy, prescription of tranexamic acid, blood transfusions). We will calculate basic demographics (e.g. age, mortality rates) for the patient cohort and compare these to previously published data e.g. from the Trauma Audit Network (TARN) audit. We will also look at how individual criteria overlap to see whether we can identify any redundancy in the list of data sources.
- Sources of patient data required by the algorithm will be integrated into a “real-time” digital platform by processing HL-7 messaging from individual hospital IT systems. This will expand on a pre-existing software platform (developed for the HAVEN Study, <https://ora.ox.ac.uk/objects/uuid:322561c7-866e-4c1e-bcc1-65da4da477fb>) which listens to hospital wide computer systems, integrating relevant data into a real-time research database.
- Using the real-time database, we will implement the algorithm on a lightweight web interface (R Shiny). The interface will include the ability for users to input additional data from the notes review (details below).
- Research nurses will use the interface to identify (up to 200) patients who are potentially bleeding and review their free-text notes in the electronic patient record, notifying attending clinicians when there is no documentation of bleeding. Using the additional clinical information in patients’ notes, the nurses will record whether they agree with the output of the algorithm. Where the algorithm has incorrectly identified patients as having bled, the nurses will record the reasons for bleeding based on the clinical information in the notes.
- The expert panel will review the results of the notes review and refine the algorithm to increase its specificity.
- The expert panel will not have any access to confidential patient information.

9.2 Consent patients identified by system for use of surplus routine blood samples in research analysis.

In the final three months of the study, we will prospectively test the accuracy of the algorithm and the feasibility of using the real-time platform for consenting patients to use their data and routine blood samples for future research.

When the algorithm identifies that a patient has met the criteria for bleeding, the platform will:

- Allocate the patient a RE-BLEED study ID.

- Electronic Hospital Record (EHR) data for this entire encounter will be retained in the study database and when the encounter ends the record will be pseudo-anonymised.
- A notification will be sent to the main hospital laboratory requesting that their (left-over) blood samples, once all clinical testing has been completed as part of routine clinical care, be retained for use in the study, pending patient consent. Where consent is not given, the samples will be destroyed as per local protocols.

In order to be able to screen all patients in the hospital, the system must collect data for all adult patients from their admission to their discharge. The records of adult patients admitted to the hospital who do not meet the eligibility at any point during their admission will be destroyed at the point they are discharged from hospital.

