2 LAY SUMMARY

Bleeding affects up to 40% of all trauma patients, up to 30% of all surgery patients and is one of the commonest causes of death for women giving birth. The presentation and features of bleeding are

different between patients – in some cases bleeding is very obvious to recognise, but in other cases bleeding is more “hidden”, for example in the stomach. Bleeding must be stopped promptly to prevent severe illness or death.

Many studies have shown differences in how patients who bleed are treated. There is also variation in how individual patients respond to the same treatment, with some patients doing better than others. Understanding how variation in practice and patient characteristics affect outcomes will help us design and test improvements in care.

Patients in hospital have regular tests that measure levels of the different types of cells in their blood and its ability to clot. For example, a drop in red blood cells can indicate that patients have suffered bleeding. More advanced blood tests are available that can provide more detailed information on why patients are bleeding and what treatments might be most effective.

This study aims to develop a real-time, hospital-wide digital system to identify patients in hospital who have suffered from bleeding and test whether this system could be used in the future to potentially identify patients to recruit into trials of new treatments or blood tests.

To do this, we will:

- Assemble a panel of experts to identify criteria (for example, specific blood test results and drug prescriptions) that could indicate a patient has suffered from bleeding
- Use historical electronic patient records to test how well these criteria identify patients who have received treatments for bleeding (blood transfusion)
- Develop and refine a web-based digital system where the most useful criteria can be applied in “real-time” to identify bleeding patients
- Test how well the digital platform identifies bleeding patients
- Test whether a significant number of patients identified by the digital platform are willing to allow their routine blood samples tested for blood clotting and endothelial factors.

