6 OBJECTIVES AND OUTCOME MEASURES

Objectives	Outcome Measures	Timepoint(s) of evaluation of this outcome measure (if applicable)
Primary		
To test whether a digital platform can efficiently identify patients who have suffered a bleeding event and	At least 200 patients correctly identified as having suffered bleeding, of which 40 (20%) provide consent	End of study

are willing to consent for the routine blood samples to be used in research.
		

Secondary
		

 1. To conduct a Delphi process with an expert panel to identify criteria that could be applied in the electronic patient record to identify patients with acquired bleeding 2. To use 10 years’ of retrospective data to map bleeding criteria to appropriate data fields within the electronic patient record data sources 3. To encode bleeding criteria into a real-time “algorithm” and display results within a digital web-based platform 4. To measure and refine the accuracy of the algorithm, by manual review of free-text notes of patients identified as bleeding 5. Assess the feasibility of sample sequestering by the lab 6. Assess the feasibility of performing blood clotting and endothelial factor analysis on the sequestered samples. 	
 1. List of bleeding criteria 2. Bleeding criteria mapped to appropriate data fields on the electronic patient record 3. Digital platform capable of identifying bleeding patients in real-time 4. Algorithm accuracy before/after refinement 5. List of unique challenges faced by the laboratory team during blood sample retention and analysis 6. Numbers of samples retained and additional blood clotting and endothelial factor results captured from the retained samples. 	
End of study

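### If transfusion request stays a criterion, retrospective sensitivity is high largely by construction in transfused patients, and one overall figure could hide low detection of untransfused bleeding

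*Protocol*

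**What the plan says.** Protocol section 9.1 asks a Delphi panel to "identify a set of starting criteria (algorithm) e.g. transfusion request or absolute/drop in Hb". At this stage "we will aim to agree broad criteria that maximise the sensitivity of the algorithm". The criteria are mapped to routine data and combined into one algorithm, which is then tested on the retrospective extract: "We will assess its sensitivity to identify patients who have received treatments/investigations for bleeding (e.g. urgent endoscopy, prescription of tranexamic acid, blood transfusions". The lay summary (section 2) describes the same test and names only transfusion: "Use historical electronic patient records to test how well these criteria identify patients who have received treatments for bleeding (blood transfusion".

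Section 9.1 plans one check on overlap: "We will also look at how individual criteria overlap to see whether we can identify any redundancy in the list of data sources". Section 11.1.3 adds retrospective subgroups by clinical setting (obstetric, gastro-intestinal, emergency surgery, trauma). Accuracy as a secondary objective is handled separately in section 6: "To measure and refine the accuracy of the algorithm, by manual review of free-text notes of patients identified as bleeding".

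**The concern.** A sensitivity estimate is informative when the reference event is established independently of the test. Here an example criterion (a request for blood) and an example reference event (blood given) are two records of nearly the same clinical action. If the request is in the algorithm, a transfused patient is flagged almost automatically, and that says little about whether the algorithm recognises bleeding.

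The overlap reaches beyond patients whose only reference event is transfusion. Someone who had urgent endoscopy or tranexamic acid and also had a transfusion request is flagged by the same route. The lay summary also lists drug prescriptions as possible criteria. If tranexamic acid prescription became one, the same problem would arise for that reference event.

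What is at stake is the reading of the development result. The first-stage criteria are meant to be sensitive, and section 9.5 aims at bleeding of any severity, which includes bleeding that is never transfused. An overall figure dominated by transfused patients would not show how well the rest are found.

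**Working it through.** **1. The plan's own figure.** Sensitivity enters a calculation only in section 11.2.2: about 250 bleeding events at an assumed sensitivity of 80% give 250 × 0.80 = 200 records to review. This reproduces. The 80% is a planning assumption for the prospective review and is not tied to the retrospective test. It serves below only as a benchmark.

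**2. Would the planned analyses expose the overlap?**
- The overlap check in section 9.1 compares criteria with one another, to find redundant data sources. It does not compare criteria with reference events.
- The subgroups in section 11.1.3 are by setting. None is by transfusion status.
- The prospective review starts from flagged patients: "Research nurses will use the interface to identify (up to 200) patients who are potentially bleeding and review their free-text notes". It shows how many flags are right and does not count missed bleeds.

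**3. How much could an overall figure hide?** Let
- t = share of reference patients who were transfused (not in the documents; assumed),
- f = share of transfused reference patients who are flagged (assumed: 100%, or 90% to allow for requests that are not captured),
- s = sensitivity in untransfused reference patients (unknown).

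Overall sensitivity = t·f + (1 − t)·s.

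Forward, with t = 0.5 and f = 1:
- s = 0.30 gives 0.50 + 0.50 × 0.30 = 0.65
- s = 0.70 gives 0.50 + 0.50 × 0.70 = 0.85

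Backward, from an overall 0.80: s = (0.80 − t·f)/(1 − t).

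| t | s if f = 100% | s if f = 90% |
|---|---|---|
| 20% | 0.60/0.80 = 75% | 0.62/0.80 = 77.5% |
| 30% | 0.50/0.70 = 71% | 0.53/0.70 = 76% |
| 50% | 0.30/0.50 = 60% | 0.35/0.50 = 70% |
| 70% | 0.10/0.30 = 33% | 0.17/0.30 = 57% |
| 80% | 0.00/0.20 = 0% | 0.08/0.20 = 40% |

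The masking is small when few reference patients were transfused and large when most were.

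**4. What the model does not separate.** Some transfused patients would be flagged by the haemoglobin criterion anyway, so not all of f comes from the overlap. Only a run with transfusion request left out tells the two apart.

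**The case against.** The strongest reply is that the protocol does not fix the error. Both lists in section 9.1 are examples, the panel decides the criteria, and nothing says that only one undifferentiated figure will be reported. That is inferred from a single combined algorithm being tested against a mixed list. Section 11 promises a statistical analysis plan, not shown here, which could stratify. This stands, and it makes the point conditional. It does not remove it: the overlapping pair is the protocol's own choice of examples, and no safeguard is stated if the panel keeps the criterion.

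A second reply is that section 9.1 already describes the measure as sensitivity for treated or investigated patients, not for all bleeding. That is fair as to wording. It does not help a reader see how much of the figure comes from transfused patients.

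Third, the redundancy check could show how many flagged patients met only the transfusion request. That would be partial evidence of dependence on the request, but it is not confined to reference patients and does not give sensitivity without it.

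Two stronger readings are tempting. A reader might infer that the whole retrospective sensitivity is circular. The documents do not support that: a request is not the same as a transfusion given, and reference patients with endoscopy or tranexamic acid but no transfusion request are not flagged through that criterion. A reader might also infer that the feasibility result is undermined. It is not: the primary outcome counts correctly identified and consenting patients, the accuracy outcome rests on notes review, and section 11.4 sets no decision point.

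**Conclusion.** The point holds in conditional form. If transfusion request is kept, retrospective sensitivity in transfused patients will be high largely by construction, and one overall figure could conceal low detection of untransfused bleeding. The same applies to tranexamic acid if that prescription becomes a criterion.

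The size cannot be computed from the documents, because t, f and s are all absent. The values above show what is possible, not what is likely. They rest on the assumed transfused share, on 90% to 100% of transfused reference patients being flagged, and on a single figure being reported. The consequence is confined to how the retrospective development result is interpreted. The change is worth making because it is cheap, but the study's conclusions on consent and on notes-review accuracy do not depend on it.

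**What to change.** In section 9.1, state that retrospective sensitivity will be:
- reported separately for transfused and untransfused reference patients;
- recomputed with transfusion request removed from the algorithm, and likewise with any other criterion that matches a reference event removed (for example tranexamic acid prescription, if adopted);
- described, for the transfused group, as sensitivity for transfused patients only. The lay summary's account of this test should be brought into line.

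A split by type of reference event alone would not be enough. Endoscopy patients with a transfusion request would still be flagged through it, and detection in untransfused patients would still not be reported.

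The cost is a few extra runs on data already held, with no change to recruitment, consent or sample handling. The drawback is that the reported sensitivity will probably be lower.
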